7. STUDY DESIGN AND DURATION

7.1. Study design and justification

This is a prospective, multi-centre, **individually randomised controlled open-label trial**. Approximately 1600 patients will be randomised in the trial in up to 10 investigational sites in the European region. Patients will be followed at day 14 and day 30 after randomisation. In a subset of patients, follow up will be extended to time points 3 and 6 months.

Enrolment will be competitive across sites.

Justification of the design. The aim is to deliver a study outcome that is **valid** (absence of bias), **precise** (sufficiently powered to achieve clinically relevant absence and presence of difference), and **generalizable** (recognizable population). The study needs to be **feasible** in terms of costs

(determined by number of study sites and number of tests to be performed), with an easy patient enrolment and an achievable burden on laboratories in both adult and paediatric sites. Therefore, although an **individually randomised trial** - in contrast to cluster randomisation - requires informed consent from all recruited patients fulfilling inclusion criteria prior to performing the test. This approach has several advantages: 1. Internal validity of the trial is guaranteed by the randomisation, whereas in cluster-randomised trials, patient selection criteria can be difficult to apply in a consistent manner, inducing a risk of selection bias; 2. Required sample size is lower compared to a cluster-randomised trial; 3. Recognizable population can be realized, although generalizability will always be lower compared to enrolling all-comers; 4. Feasibility: compared to a cluster-randomised trial, a lower sample size is needed, reducing costs for study execution; fewer hospitals, fewer patients, and a lesser burden on labs because tests are only performed in 50% of enrolled patients instead of 100% of all-comers. Moreover, although requirement of informed consent to be obtained at the ER could be considered as a drawback of this design, it in fact may help in enrolling the pursued patient population for this specific trial. We aim for patients in which the result of the rapid syndromic testing can guide clinical decision making. This implies that there is also time for obtaining informed consent.

In choosing the primary endpoints the following considerations were made:

- The composite endpoint is designed to capture the relevant outcomes and will be combined for analysis
- It needs to be ensured that the non-inferiority endpoint is not positively impacted by direct effects of the intervention such as decisions to initiate or withhold antibiotic treatment or early discharge from the ER or hospital. E.g. if we would include hospitalisation days in the non-inferiority endpoint, we run the risk of 'compensating' the putative adverse effects.
- **Hierarchical nested design:** Superiority primary endpoints are tested first. Only if superiority to at least one of the two superiority endpoints is confirmed, is the non-inferiority safety endpoint taken into consideration [22]
- Because of the non-blinded nature of the study, outcomes should be defined objectively, so e.g. we cannot use cause-specific re-admission or cause-specific death.
- Reassessment when other microbiological results are available. Discrepant results should be handled by the treating physician based on best practice
- Different time windows have been chosen because i) impact of rapid syndromic testing on hospitalisation / antibiotics is immediate. ii) Shorter follow-up increases power for difference of 1 day. iii) Adverse outcomes may reflect late sequelae.

7.2. Study duration

The study will encompass at least 2 influenza seasons (autumn/winter months) in Europe, however timelines might be extended related to the COVID-19 situation.

Justification. i) most CA-ARTI occur in autumn/winter months. ii) Timeframes allow for training, initiation and patient follow up. iii) To achieve an adequate sample size iv) Fluctuations in microbiological epidemiology of CA-ARTI (seasonal outbreaks *Mycoplasma*, *Bordetella*, variability on virus lineages, pneumococcal serotypes, etc.) are better represented with more than one season.

8. STUDY POPULATION

8.1. Study population

Adults (≥18 years old) presenting at the Emergency Room in selected participating sites with CA-ARTI and able to give informed consent.

8.2. Inclusion criteria

1. **Adults** (≥18 years old) presenting to the **Emergency Room** with an **acute illness** (present for **14 days or less**) with **cough, and** with at least 1 other lower respiratory tract **symptom** or **clinical sign** at physical examination:
 - Sputum production,
 - Breathlessness,
 - Chest discomfort or chest pain,
 - Wheeze,
 - Crackles,
 - Self-reported dyspnoea or documented fever;
 - Documented hypoxemia (adjusting definition for chronic oxygen therapy users, method of measurement) **and no alternative explanation** (infection, such as sinusitis; other, such as asthma).
2. **Managing medical team considers** early in the diagnostic process:
 - a. to treat patient with antibiotics and/or to hospitalise patient

AND

 - b. that the rapid syndromic diagnostic test result can be awaited up to a maximum of 4 hours before the decision to discharge the patient or to initiate antibiotic therapy.

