10.1. Screening and enrolment

Patients entering the emergency room will be screened for study. When exclusion criteria 7-9 are unknown at the time of screening, patients will be enrolled nonetheless when they meet these inclusion criteria. After informed consent is obtained, remaining exclusion criteria will be checked.

The health status of patients might rapidly deteriorate between entering the emergency room and randomisation. Therefore, all eligibility criteria need to be re-evaluated and confirmed prior to the decision to randomise the patient.

Screen failures are defined as patients who were found eligible per screening and have given their consent to participate in the trial, but meet exclusion criteria 7 to 9 or did not meet all inclusion criteria anymore, during the evaluation of exclusion criteria 7 to 9. Of note, no diagnostic procedures such as chest radiograph will be performed for the purpose of checking eligibility criteria, only if indicated as standard of care. E.g. “if a chest radiograph is not deemed necessary by the treating physician, a pneumonia (exclusion criterion 7) cannot be excluded, but the patient can still be enrolled as there is no ‘radiologically confirmed acute lobar pneumonia’. When all criteria are met, the patient will be randomised (see next paragraph).

Figure 1. Study flowchart

*Radiologically confirmed acute lobar pneumonia, known or suspected *Pneumocystis jirovecii* pneumonia or active tuberculosis, alternative noninfectious diagnosis that explains clinical symptoms (pulmonary embolism, alveolar hemorrhage, acute heart failure, lung cancer)

ER: emergency room

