10.4. Clinical data set

Inclusion. Check for inclusion and exclusion criteria and randomisation. Informed Consent Form.**Baseline registration and investigations.**

Signs and symptoms at ER and management plan

Participant background

Vaccination

Co-morbidities and chronic medication

Standard of care haematology and biochemistry

EQ-5D-5L questionnaire

Management: Clinical decision after randomisation and initial results

Investigations: respiratory, urine, faeces, blood, SARS-CoV-2, radiology (only when standard of care)

Day 14: symptoms, EQ-5D-5L questionnaire

Day 30: symptoms, EQ-5D-5L questionnaire

Month 3 (if applicable): symptoms, EQ-5D-5L questionnaire

Month 6 (if applicable): symptoms, EQ-5D-5L questionnaire

Outcomes and safety:

Antibiotic treatment

Antiviral and antifungal agents

Hospital course

Device deficiency

(Severe) Adverse Event

Deviation

End of study

Table 1. Visit Schedule

Procedures	Screening	Enrollment	Hospitalization Period ^e	Face to face, on line questionnaire or phone call		Phone call Extended FU	Phone call Extended FU
	Pre- study procedures	Day 1	> Day 1	Day 14	Day 30	3 months ^f	6 months ^f
	Day 1						
Informed consent	X						
Eligibility criteria	X						
Demographics ^a	X						
Baseline assessment ^b	X						
Vaccination status	X						
Comorbidities and chronic medications	X						
Hospital course ^c		X	X ^e				
Microbiological testing ^d		X	X				
Concomitant therapy review	X	X	X ^e	X	X	X ^f	X ^f
Symptoms review and hospitalizations	X	X	X ^e	X	X	X ^f	X ^f
Quality of life questionnaire EQ5D		X		X	X	X ^f	X ^f

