13.2. Analysis populations

A statistical analysis plan will be prepared after protocol approval and once site selection process has been initiated.

The main analyses will be performed for the total population

Analyses will be stratified by:

- age groups (i.e. 18-49, 50-65, >65)
- clinical syndrome: exacerbation of chronic pulmonary disease, influenza-like illness, laryngitis/laryngotracheitis (croup), acute bronchitis
- risk factors. Patient groups at risk for developing severe disease are well known, such as the elderly, patients with chronic pulmonary, cardiovascular or metabolic disease or immunocompromised patients. Clinical predictors of severity are also well known. Still,

within risk groups may exist the uncertainty whether to hospitalise and/or to treat and the impact of testing may be assessed.

- Vaccination status. Influenza. Pneumococcal.

The primary analysis will follow the intention-to-treat principle in which groups are compared based on the allocated regimen. In the per protocol analysis we will exclude participants not receiving the test according to the randomised regimen (e.g. randomised to rapid syndromic testing but not receiving the test).

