13.3. Primary study parameter(s)

Descriptive statistics will be produced and tabular summaries will be presented, stratified according to the allocated group (rapid syndromic testing vs. control). Categorical data will be summarized by the number and percentage of patients in each category. Appropriate summary statistics will be used for continuous variables depending on the distributional assumptions. These include measures of central tendency (mean or median) and dispersion (standard deviation or inter-quartile range).

‘Days on antibiotic treatment’ and ‘Days alive out of the hospital’ will be analysed using a linear regression analysis, including as covariates stratification by age groups and predefined risk factors. Upfront we may expect that the assumption of normally distributed residuals is violated, in which case we will determine the confidence interval by bootstrapping.

Adverse outcome will be analysed using Cox proportional hazards regression adjusted for age groups and predefined risk factors. Risk differences and 90% CI will be inferred by comparing the cumulative incidence of failure at day 30 from the Cox model and bootstrapping for the confidence interval. A 90% CI will be used to be compatible with a one-sided alpha of 0.05.

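### Whether antibiotics, admission or both were being considered before the test is established before randomisation, but it is not named as a covariate or stratification factor; adding it is a low-cost precision gain

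*Combined protocol and SAP*

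**What the plan says.** Protocol section 8.2, criterion 2a, requires that the managing team considers, early in the work-up, "to treat patient with antibiotics and/or to hospitalise patient". Criterion 2b adds that the test result can be awaited before the decision is made.

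Section 10.1 fixes the timing: "all eligibility criteria need to be re-evaluated and confirmed prior to the decision to randomise the patient". Section 10.2 has randomisation follow verification of eligibility, through the eCRF module, stratified by centre only. Section 10.4 lists "Signs and symptoms at ER and management plan" among the baseline items and, separately, "Management: Clinical decision after randomisation and initial results".

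In section 13.3, antibiotic days and days alive out of hospital "will be analysed using a linear regression analysis, including as covariates stratification by age groups and predefined risk factors". For the safety endpoint, "Adverse outcome will be analysed using Cox proportional hazards regression adjusted for age groups and predefined risk factors". Section 13.2 lists age group, clinical syndrome, risk factors and vaccination status for the stratified analyses. It describes risk factors as groups prone to severe disease (older age, chronic disease, immunocompromise) and adds that "Clinical predictors of severity are also well known", without closing the list. It leaves the SAP to be prepared later.

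**The concern.** The trial asks whether the test changes two decisions: admit or not, and start antibiotics or not. Criterion 2a records which of these was open before the test. A patient considered only for antibiotics probably has few hospital days to save, and one considered only for admission probably has few antibiotic days to save. The item is therefore a plausible prognostic factor for both superiority endpoints, and it may mark where the test can act.

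The plan obtains this information to establish eligibility but does not name it in any model or stratified analysis, and randomisation does not balance it. At stake are some width in two confidence intervals and a subgroup that would help interpret a weak overall effect.

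**Working it through.** **1. Reproduce the plan's sample sizes (section 13.1).** For days alive out of hospital: two-sided alpha 0.025, power 0.90, difference 1 day, correction 1.15.

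n per arm = 1.15 × 2 × [SD × (2.2414 + 1.2816) / 1]². At SD 4 this is 1.15 × 397.16 = 456.7, so 457, as stated. SDs of 3, 5, 6 and 7 give 257, 714, 1028 and 1399, matching the plan's table.

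For adverse outcome (10% in both arms, margin 5%, one-sided alpha 0.05, power 0.95): 2 × 0.10 × 0.90 × (1.645 + 1.645)² / 0.05² rounds up to 780 per arm, as stated. This endpoint sets N: 2 × 780 = 1560, raised to 1600 for drop-out.

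**2. How much might criterion 2a explain?** The documents do not say, so this is an assumption. For a yes/no split with share q and a gap of d days, R² = q(1 − q)d²/SD². At SD 4:

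| Share considered for admission | d = 2 | d = 3 | d = 4 |
|---|---|---|---|
| 0.50 | 0.06 | 0.14 | 0.25 |
| 0.85 | 0.03 | 0.07 | 0.13 |
| 0.90 | 0.02 | 0.05 | 0.09 |

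These are marginal values; age and risk factors, already in the model, would absorb part of them. I use 0.02 to 0.30 as the range for what is added beyond those covariates. The top of the range is generous: it needs a gap above 4 days even with an even split.

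**3. Effect on interval width.** The residual SD is SD × √(1 − R²), so the interval narrows by 1 − √(1 − R²): 1% at R² 0.02, 5% at 0.10 and 16% at 0.30. At SD 4 and 780 per arm, with the 1.15 correction, the 97.5% half-width is 2.2414 × 4 × √(2 × 1.15/780) = 0.49 day. It falls to 0.46 at R² 0.10 and 0.41 at R² 0.30.

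**4. Effect on power for 1 day at 780 per arm.** Power = Φ(1/SE − 2.2414), with SE = SD × √(1 − R²) × √(2 × 1.15/780). The stated SD is treated as what remains after age and risk factors.

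| SD | R² = 0 | R² = 0.10 | R² = 0.30 |
|---|---|---|---|
| 4 | 99.1% | 99.5% | 99.9% |
| 5 | 92.5% | 95.0% | 98.5% |
| 6 | 79.6% | 84.0% | 92.3% |
| 7 | 65.2% | 70.3% | 81.7% |

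Unadjusted power stays at or above 90% up to SD = √(780/2.3)/3.523 = 5.2 days.

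**5. Chance imbalance.** With an even split, the SE of the between-arm difference in share is √(2 × 0.25/780) = 2.5 percentage points. A 3- to 5-day gap turns that into 0.08 to 0.13 day, which the unadjusted interval already covers.

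The plan gives no SD for antibiotic days, only that it should be smaller, so no separate figure is computed for that endpoint. None is computed for adverse outcome.

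**The case against.** **The covariate list is open.** Predefined risk factors are not enumerated and the SAP is still to come. The risk-factor bullet in section 13.2 even mentions uncertainty over admission or treatment within risk groups. This stands in part: the plan has not decided to leave the item out. But nothing names it, and the risk factors described concern severe disease rather than which decision is open.

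**Considering is not intending.** Criteria 2a and 2b together select patients whose management is undecided, so the groups may differ less than firm intentions would. This stands, and is why the range in R² starts at 0.02.

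**The gain is not needed for power.** At the planning SD this is correct. The planning SD, however, comes from hospitalised pneumonia patients. Section 13.1 calls the distribution in the target population unknown, although it expects less variability there.

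Three stronger readings are tempting but unsupported:

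- A reader might infer that the plan discards the strongest predictor of both endpoints. The documents give no correlation for this or any other covariate.
- A reader might infer that the entry could be made after allocation is known and so be contaminated in an open-label trial. Sections 10.1, 10.2 and 10.4 place the eligibility check and the baseline plan before allocation, apart from the later decision. Only an explicit eCRF lock and the coding are unstated.
- A reader might take the share considered for admission from section 8.4, assume gaps of 3 to 5 days, and conclude that adjustment is worth 12% to 64% more patients. Section 8.4 concerns actual hospitalisation among all such emergency patients at a site, not enrolled patients considered for admission. No passage supports the gaps.

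**Conclusion.** The point holds as a precision recommendation. Naming the criterion 2a answer as a covariate would narrow the interval for days alive out of hospital by about 1% to 16%, if it explains 2% to 30% of the variance beyond age and risk factors. Antibiotic days would gain in the same proportion under the same assumed R². That R² is an assumption; the documents neither support nor exclude it.

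The sample size is unaffected. For an average effect of 1 day, power changes materially only if the SD exceeds about 5 days. The randomised comparison is valid without the adjustment, and chance imbalance is not a bias. The other gain is interpretive: results by group would show whether an effect is concentrated where the relevant decision was open.

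**What to change.** - Record criterion 2a as two yes/no eCRF fields, 'antibiotics considered' and 'admission considered'. Complete them with the eligibility check before the randomisation module opens, and keep them separate from the item on the decision taken after randomisation.
- In section 13.3 and the SAP, name both fields as covariates in the models for antibiotic days and days alive out of hospital. Adding them to the Cox model is optional.
- Add the three resulting groups (antibiotics only, admission only, both) to the stratified analyses in section 13.2.

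The cost is one eCRF ordering rule, short additions to sections 13.2 and 13.3 and the SAP, and two degrees of freedom per model. No patients or visits are added. The fields must be in place when patients are enrolled, because an answer free of knowledge of the allocation cannot be reliably recovered afterwards.

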8.3. Exclusion criteria

1. Development of ARTI more than 48 hours after hospital admission (**hospital acquired**);
2. Patients with **cystic fibrosis**;
3. Less than **14 days** since the last episode of respiratory tract infection;
4. Pregnancy (confirmed by pregnancy test) and breastfeeding;
5. Any clinically significant abnormality identified at the time of screening that in the judgment of the Investigator would preclude safe completion of the study or constrain endpoints assessment such as major systemic diseases or patients with short life expectancy;
6. Inability to obtain informed consent from a competent patient.

Based on standard of care microbiological diagnosis and thoracic imaging (when indicated):

7. Radiologically confirmed acute lobar pneumonia;
8. Known or suspected *Pneumocystis jirovecii* pneumonia or active tuberculosis;

9. Alternative noninfectious diagnosis that explains clinical symptoms (pulmonary embolism, alveolar hemorrhage, acute heart failure, lung cancer).

Patients participating in interventional therapeutic studies related to COVID-19 are not considered *a priori* an exclusion criteria if it does not interfere with randomisation to the diagnostic intervention and the primary outcomes of the ADEQUATE clinical study. Compatibility will be evaluated individually.

8.4. Recommended Study site selection criteria

- Does not currently use equivalent rapid testing routinely in patients with CA-ARTI at the ER (rapid defined as time from sample collection to result interpretation by the physician within 4 hours).
- At least 25% of CA-ARTI patients seen at ER are not hospitalised.
-
- Microbiology lab is capable of performing molecular testing.
- Highly motivated and GCP-trained local Principal Investigator. Clinical research nurse.
- **Geographical balance:** We will prioritize EU Member States and H2020 Associated Countries with **high and medium antibiotic use** and with a range of **country level income and antibiotic stewardship programs** (if present, the antibiotic stewardship program will be documented, including the list of participant roles). Variations in **microbiological aetiologies and vaccination policies** will be taken into consideration.

9. DIAGNOSTIC INTERVENTION

9.1. Description of the test and Intended use

Two rapid syndromic diagnostic tests, to be allocated according to clinical syndrome, age and available sample. The results of this test should not be used as the sole basis for diagnosis, treatment, or other patient management decisions.

- **BioFire FilmArray Respiratory Panel 2.1 plus (RP2.1plus):** Nasopharyngeal swab
- **BioFire FilmArray Pneumonia Panel plus (PP):** Sputum (and/or ETA or BAL sample)

The **FilmArray Respiratory Panel 2.1 plus (RP2.1 plus)** is a multiplexed nucleic acid test intended for use with FilmArray® 2.1 or FilmArray® Torch systems for the simultaneous qualitative detection and identification of multiple respiratory viral and bacterial nucleic acids in nasopharyngeal swabs (NPS) obtained from individuals suspected of respiratory tract infections. The test is FDA approved.

Virus: Adenovirus, Coronavirus (229 E, HKU1, NL63, OC43, SARS-CoV-2), human Metapneumovirus, Human Rhinovirus/Enterovirus, Influenza A, including subtypes H1, H1-2009, and H3, Influenza B, Middle East Respiratory Syndrome Coronavirus (MERS-CoV), Parainfluenza Virus (1, 2, 3, 4), Respiratory Syncytial Virus. **Bacteria:** *Bordetella parapertussis* (IS1001), *Bordetella pertussis* (ptxP), *Chlamydia pneumoniae*, *Mycoplasma pneumoniae*

The **FilmArray® Pneumonia Panel plus** is a multiplexed nucleic acid test intended for use with FilmArray® 2.0, or FilmArray® Torch systems for the simultaneous detection and identification of

multiple respiratory viral and bacterial nucleic acids, as well as selected antimicrobial resistance genes, in sputum-like specimens (induced or expectorated sputum, or endotracheal aspirates) or Broncho alveolar lavage (BAL)-like specimens (BAL or mini-BAL) obtained from individuals suspected of lower respiratory tract infection.

The following **bacteria** are reported **semi-quantitatively** with bins representing approximately 10^4 , 10^5 , 10^6 , or $\geq 10^7$ genomic copies of bacterial nucleic acid per milliliter (copies/mL) of specimen, to aid in estimating relative abundance of nucleic acid from these common bacteria within a specimen:

Acinetobacter calcoaceticus-baumannii complex, *Klebsiella oxytoca*, *Serratia marcescens*, *Enterobacter cloacae complex*, *Klebsiella pneumoniae*, *Staphylococcus aureus*, *Escherichia coli*, *Moraxella catarrhalis*, *Streptococcus agalactiae*, *Haemophilus influenzae*, *Proteus spp.*, *Streptococcus pneumoniae*, *Klebsiella aerogenes*, *Pseudomonas aeruginosa*, *Streptococcus pyogenes*

The following atypical bacteria, viruses, and antimicrobial resistance genes are reported **qualitatively**:

Atypical Bacteria *Chlamydia pneumoniae*, *Legionella pneumophila*, *Mycoplasma pneumoniae*

Viruses: Adenovirus, Human Rhinovirus/Enterovirus, Middle East Respiratory Syndrome Coronavirus (MERS-CoV), Coronavirus, Influenza A, Parainfluenza Virus, Human Metapneumovirus, Influenza B, Respiratory Syncytial Virus

Antimicrobial Resistance Genes: CTX-M, NDM, mecA/C and MREJ, IMP OXA-48-like, KPC VIM

